11. Recruitment through a list of research subjects who have previously been recruited by our study team and have agreed to recontact for future studies.
12. Recruitment through materials distributed to providers who care for NAFLD patients outside of the Partners System.
13. Recruitment through the Research Match (Vanderbilt Recruitment Tool)

Subjects who express interest will be pre-screened via a REDCap questionnaire or phone.

IV. SUBJECT RECRUITMENT

A. Trial Population

Subjects responding to the initial recruitment advertisements will undergo initial screening and if deemed potentially eligible for participation, they will be contacted by telephone and invited to participate in a screening visit. Based on a conservative assumption of 60% rate of either screening failure or subjects declining to participate in a research study, we expect to screen 200 adult subjects and enroll a total of 80 subjects with confirmed NAFLD without cirrhosis.

B. Consent

All subjects will receive the consent form for the study as well as the Human Subject's Bill of Rights. These documents will be read by the study subjects and also reviewed carefully by the study subject with a clinician on the research staff, prior to participating in the study. Any questions, concerns, or ambiguities will be appropriately clarified by the study clinician prior to the patient signing consent. Potential study subjects will sign informed consent and only then will they begin participation in the study. If new information is ascertained during the study, we will modify our consent and re-consent our patients accordingly.

C. Randomization

After baseline testing, 80 subjects who meet all eligibility criteria will be randomized to one of two treatments for 6 months: 1) low-dose aspirin (81mg per day), or 2) identical, blinded placebo pills.

Study Endpoints	Month 0	Month 6
Intrahepatic Lipids (1H-MRS)	✓	✓
Inflammation / Fibrosis (LiverMultiScan, Fibroscan)	✓	✓
Specialized Proresolving Mediators (SPMs)	✓	✓
Untargeted Eicosanoids, Inflammatory Markers	✓	✓
PNPLA3 rs738409 genotype	✓	

*All subjects will have NAFLD with fibrosis stage 0-3 (F0-3) confirmed by prior clinical liver biopsy or by validated imaging modality.

V. STUDY PROCEDURES:

A. Overview of Study Design.

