To ensure data entry accuracy, peer review of source documentation and case report forms in REDCap will be completed following MGB Study Data Management and Quality Assurance Plan Guidelines. Research coordinators will exchange subject files and review informed consents, case report forms, and adverse event logs for accuracy and completeness. Additionally, eCRFs in REDCap will be reviewed for accuracy and completeness using source data verification.

C. Statistical Analysis and Power

Data Analysis Plan:

This statistical analysis plan will be finalized before database lock. Baseline data between groups will be compared using chi-squared test or Fisher's exact test for categorical variables, and using ANOVA for continuous variables, with any non-normally distributed data log-transformed prior to analysis. If significant baseline group imbalance is detected on any particular variable, that variable will be included as a covariate in the analyses.

Absolute and relative changes in continuous outcomes between treatment groups will be calculated using analysis of covariance (ANCOVA), with treatment group at randomization included as a fixed effect, and the baseline value of the relevant outcome included as a covariate. Logistic regression will be used for binary outcomes (i.e., achievement of $\geq 30\%$ relative HFF reduction). For the primary analysis, all study endpoints will be analyzed using an intention-to-treat approach, using data from all randomly assigned participants in the full analysis set. The primary analysis will assume that missing data were missing at random³⁸, and data augmentation for missing observations will be conducted via multiple imputation, using all available non-missing data of the outcome measurement from the same treatment arm.

We will also utilize data from all participants who adhere to therapy as assigned and complete the final, 6-month visit for study outcomes (i.e., the per protocol analysis set).

We will conduct the following subgroup and sensitivity analyses for the primary and key secondary endpoints:

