To address potential confounding due to meaningful weight loss between baseline and month 6, we will exclude any participant who loses $\geq 3\%$ body weight during the 6-month study period. We will construct separate, multivariable-adjusted regression models accounting for *a priori* defined clinical confounders, including age, sex, race/ethnicity, type 2 diabetes status at baseline, fasting insulin level at baseline, body weight and visceral adipose tissue (VAT) volume, as previously recommended for NAFLD clinical trials⁸. We will also repeat the analyses with missing data for primary and key secondary endpoints considered as nonresponses, by carrying forward the baseline values. We will also conduct subgroup analyses for the endpoints of

absolute change in HFF by MRS (primary endpoint) and relative HFF change by MRS (key secondary endpoint) in participants with significant, stage 2-3 fibrosis at baseline.

Sample Size, Statistical Power & Multiplicity Testing:

We anticipate a conservative drop-out rate of approximately 15%, thus we estimate an effective sample size of 68 patients. Based on prior studies of a dietary intervention for hepatic steatosis (Ryan et al.³⁹), and data from a meta-analysis of oral omega-3 supplementation and hepatic steatosis (Parker et al.⁴⁰) we expect an effect size of 3% with the standard deviation of the change in liver fat of 2.45, by ¹H-MRS. Applying these estimates, the probability is >90% that the study will detect a treatment difference at a two-sided 0.05 significance level⁴¹. The Holm procedure to control for multiple testing will be applied to the 4 key secondary outcomes, as follows: P=0.0125 for relative change in HFF by MRS, P=0.0167 for proportion achieving ≥30 percentage point reduction in HFF by MRS, P=0.025 for absolute change in HFF by MRI-PDFF, and P=0.05 for relative change in hepatic fat by MRI-PDFF. For the other non-key secondary outcomes no multiplicity adjustments will be employed. For exploratory outcomes, no multiplicity adjustments will be used.

Definitions of Analysis Sets:

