The full analysis set includes all 80 randomized subjects. Subjects in the full analysis set will contribute to the “intention-to-treat” analysis. The as-treated set will include all participants who adhered to therapy as assigned and completed the final, 6-month study visit for study outcomes. Finally, an additional analysis set for a sensitivity analysis will be constructed with missing data for study endpoints treated as nonresponses, by carrying forward baseline values.

VI. RISKS AND DISCOMFORTS

A. Potential Risks to the Subjects

Human Subjects Involvement and Characteristics: This study will enroll 80 adults with NAFLD without cirrhosis (F0-3) between the ages of 18 and 65 years. Rationale for exclusions is discussed in the study protocol; in brief, these exclusions are designed to 1) exclude persons at greatest risk for significant adverse events, and 2) avoid confounding effects of other clinical comorbidities and/or medications.

We may send de-identified samples to a third party for analysis, such as to Metabolon, or to Qiagen, GenomeScan, or others. These specimens will not be linked to any individual identifiers associated with the patients. If we send de-identified samples to a third party, we will first generate a contract for this purpose through the hospital supply chain.

Potential risks from study drug:

- **Aspirin:** Subjects will be randomized to receive aspirin in the form of an 81mg capsule or blinded, identical placebo capsule, to be taken once daily. The risks of aspirin treatment include aspirin allergy or intolerance, with or without associated bronchospasm, gastrointestinal (GI) upset, risk for peptic ulcer disease, and bleeding, including GI bleeding, intracranial bleeding and bleeding from other sites^{11, 22-24}. We have taken several steps to minimize these potential risks. First, we have selected a low daily aspirin dose (81mg per day), which minimizes potential bleeding or ulcer-related risks, compared to higher doses. Second, we will exclude any subject with a personal history of aspirin intolerance or aspirin allergy, and anyone with a personal history indicating an increased risk for bleeding, including: personal history of bleeding or stroke, and/or history of coagulopathy and/or thrombocytopenia, and/or any subject with current use of any other anti-coagulant or antithrombotic medications. Finally, we will conduct a 3-month visit with assessment of

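### If aspirin works, the covariate-adjusted responder odds ratio would be overstated by roughly 20–40%, because ordinary logistic regression would carry 8–11 terms on perhaps 12–26 responders

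*Combined protocol and SAP*

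**What the plan says.** All of this is in section VI.C of the combined protocol and SAP, unless noted.

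- **Scope.** The Data Analysis Plan introduces the supporting analyses with "We will conduct the following subgroup and sensitivity analyses for the primary and key secondary endpoints". Section II lists four key secondary endpoints. One is binary: a relative HFF reduction of at least 30% by MRS.
- **Model.** "Logistic regression will be used for binary outcomes", with the HFF responder endpoint given as the example. No penalised or exact method, limit on model size or rule for non-convergence is named.
- **Covariates.** The adjusted models account for confounders including "age, sex, race/ethnicity, type 2 diabetes status at baseline, fasting insulin level at baseline, body weight and visceral adipose tissue (VAT) volume". The list is open-ended, and the coding of race/ethnicity is not given. A separate rule adds any variable found to be significantly imbalanced at baseline.
- **Timing.** Diabetes status and fasting insulin are tied to baseline. Body weight and VAT volume are not.
- **Missing data.** Missing outcomes are multiply imputed within arm for the primary analysis.

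**The concern.** Maximum-likelihood logistic regression with very few events per term gives log odds ratios that are biased away from zero. With sparse categories it can also give infinite coefficients. The adjusted model is meant to show whether the responder result is robust. If aspirin has a real effect, this model would report a larger odds ratio than the truth, partly because of the estimator. A reader could then take the adjusted figure as confirmation, or as a better estimate of size. With multiple imputation, a single separated completed data set could dominate the pooled estimate.

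A second, smaller matter is the unstated timing of weight and VAT. Weight is measured again at months 3 and 6, and MRI is repeated at month 6 (section V.A). Weight change is itself a secondary endpoint (section II). Adjusting for month-6 values could remove part of a treatment effect. This applies to all five endpoints.

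**Working it through.** **1. The plan's own figure.** Inputs: "The full analysis set includes all 80 randomized subjects"; "We anticipate a conservative drop-out rate of approximately 15%, thus we estimate an effective sample size of 68 patients"; "we expect an effect size of 3% with the standard deviation of the change in liver fat of 2.45". The allocation ratio is not stated ("80 subjects who meet all eligibility criteria will be randomized to one of two treatments for 6 months"), so 1:1 is assumed.

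- 80 × 0.85 = 68, or 34 per arm.
- Standard error = 2.45 × √(2/34) = 0.594, and 3/0.594 = 5.05.
- Power ≈ Φ(5.05 − 1.96) = 99.9%.

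This agrees with "the probability is >90% that the study will detect a treatment difference at a two-sided 0.05 significance level". The plan gives no figure for the responder endpoint.

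**2. Implied responders.** Take a normally distributed change, a threshold of 30% of baseline HFF (B), no mean change on placebo and a mean reduction of 3 points on aspirin. Then

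- p(aspirin) = 1 − Φ((0.3B − 3)/2.45)
- p(placebo) = 1 − Φ(0.3B/2.45)
- responders = 34 × (sum of the two)

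B is assumed, because the documents do not give it.

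| B (%) | p aspirin | p placebo | Responders of 68 | True OR |
|---|---|---|---|---|
| 8 | 0.597 | 0.164 | 25.9 | 7.6 |
| 10 | 0.500 | 0.110 | 20.8 | 8.1 |
| 12 | 0.403 | 0.071 | 16.1 | 8.9 |
| 14 | 0.312 | 0.043 | 12.1 | 10.0 |
| 20 | 0.110 | 0.007 | 4.0 | 17.2 |

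So 12–26 responders corresponds to B of about 8–14%. A higher baseline gives fewer.

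**3. Events per term** (intercept not counted). Treatment plus seven covariates is 8 terms with two-level race/ethnicity. Baseline HFF makes 9. Four-level race/ethnicity makes 10 without baseline HFF and 11 with it.

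- 8 terms: 12/8 = 1.5 to 26/8 = 3.2.
- 11 terms: 12/11 = 1.1 to 26/11 = 2.4.
- With all 80 outcomes filled in, responders are 14.2–30.4, so the range is 14.2/11 = 1.3 to 30.4/8 = 3.8.

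**4. Simulation at a true OR of 3.** N=68, 800 trials per row, covariates with no effect on outcome, four-level race split 70/15/10/5% (assumed). Medians are over fits without separation.

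| Responders | Terms | Median OR | Any separation | Aspirin OR infinite |
|---|---|---|---|---|
| 12 | 8 | 3.67 | 7.9% | 2.5% |
| 12 | 9 | 4.15 | 8.9% | 2.4% |
| 12 | 10 | 3.42 | 74.8% | 3.4% |
| 12 | 11 | 4.23 | 74.9% | 3.1% |
| 18 | 8 | 3.67 | 1.8% | 0.7% |
| 18 | 9 | 3.60 | 1.4% | 0.1% |
| 18 | 10 | 3.95 | 57.9% | 0.3% |
| 18 | 11 | 4.05 | 56.1% | 0.5% |
| 26 | 8 | 3.64 | 0% | 0% |
| 26 | 9 | 3.77 | 0.4% | 0% |
| 26 | 10 | 3.49 | 41.1% | 0% |
| 26 | 11 | 3.97 | 37.8% | 0% |

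With 8 terms the excess is 3.64/3 to 3.67/3, about +21% to +22%. With 11 terms it is 3.97/3 to 4.23/3, or +32% to +41%. The 10-term medians are less regular (+14% to +32%) and rest on fewer usable fits. A further simulation at N=68–80, with assumed placebo response of 10–20%, gave maximum-likelihood averages of 3.7–3.9 with two-level race and 3.9–4.4 with four-level race plus baseline HFF. Failures there were 0–7% and 37–75%.

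**5. No aspirin effect (true OR 1).** Medians were 0.96–1.08, and Wald type I error was 4–7%.

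**6. The plan's own effect.** True ORs of 7.6–10.0 gave medians of 11.0–13.6 with 8 terms and 13.0–16.8 with 11. At 12 responders, 30% (8 terms) or 80% (11 terms) of fits failed, and the aspirin OR was infinite in 23–25%.

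**7. Firth penalisation.** With 8 terms, N=68, a true OR of 3 and prognostic covariates, Firth medians were 2.74, 2.89 and 2.93 at 12, 18 and 26 responders (geometric means 2.90–3.09), and every fit was finite. Ordinary maximum likelihood on the same designs gave 3.84, 3.66 and 3.59.

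**The case against.** The best defence is that little depends on this model. It is a sensitivity analysis of one endpoint out of five, outside the Holm sequence, with no decision attached. The other four endpoints are continuous and use linear models. The plan also mentions separate models, which could mean several smaller ones. All of that stands and limits the reach. The smaller-models reading does not remove the point, because the plan does not say which covariates each model would hold.

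Four stronger readings are tempting, and the documents do not support them.

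- **The odds ratio is inflated whatever the truth.** It is not: step 5 shows no inflation and near-nominal type I error under no effect.
- **The adjusted result will look more convincing.** The standard error grows with the estimate. At a true OR of 3, median z was 1.58–2.16 adjusted against 1.59–2.13 unadjusted, and the adjusted p-value was the smaller one in 48–57% of trials. The problem lies in the size of the odds ratio, not in its significance.
- **Any gap from the unadjusted odds ratio is an artefact.** With prognostic covariates, a conditional odds ratio legitimately exceeds the unadjusted one. Step 4 used covariates with no effect on outcome, so the excess there is small-sample bias alone.
- **Most fits will fail.** That depends on a race/ethnicity coding the plan does not state. At a true OR of 3 with four levels, most failures lie in a race coefficient, and the aspirin coefficient is infinite in at most about 3%.

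On timing, the plan calls these covariates prespecified confounders and handles on-study weight loss by a separate exclusion analysis. Baseline values are therefore a natural reading, and repeat VAT at month 6 is inferred from the repeat MRI. The wording needs clarifying but does not prove an error.

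**Conclusion.** The point holds in conditional form. The adjusted responder model as written would have about 1–3 events per term with no safeguard. If aspirin has a real effect, its odds ratio would be overstated by roughly 20–40% at a true value of 3, and by more at the effect the plan expects. Separation is uncommon with two-level race/ethnicity and common with four levels.

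The size rests on assumptions: baseline HFF of about 8–14%, 1:1 allocation, the simulated covariate structure and the race split. Simulation error on the failure rates is up to about 2 percentage points. The primary analysis and the main, unadjusted responder analysis are not called into question.

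**What to change.** Add to section VI.C: *For the HFF responder endpoint, the covariate-adjusted model will be fitted by Firth penalised likelihood, with race/ethnicity in two prespecified levels. Log odds ratios and standard errors will be pooled across imputations by Rubin's rules.* Profile-likelihood intervals do not pool by those rules, so the plan should not promise them alongside imputation.

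If a standardised risk difference is also reported, use an intercept-corrected Firth fit. Uncorrected Firth pulls predicted risks towards 0.5. In simulation at N=68, mean predicted risk was 0.211 against 0.180 observed (placebo response 10%), and the risk difference fell to 0.211 from about 0.23 (placebo response 20%).

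In the covariate list, tie body weight and VAT volume to baseline. State that baseline HFF stays in the adjusted models for the continuous endpoints.

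The cost is a few sentences, a less familiar estimator and a somewhat smaller reported odds ratio in one sensitivity analysis. Two-level race/ethnicity also adjusts more coarsely. The plan says it will be finalised before database lock, which leaves room for the change.

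### For the continuous liver-fat endpoints, the only alternative to missing at random applied to all randomized participants, carrying baseline forward, is not guaranteed conservative and does not bound departures from that assumption

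*Combined protocol and SAP*

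**What the plan says.** Section VI.C, Data Analysis Plan, sets the primary approach: "The primary analysis will assume that missing data were missing at random". Gaps are filled by multiple imputation that draws on observed outcomes in the participant's own arm. The model is ANCOVA with treatment group and "the baseline value of the relevant outcome included as a covariate".

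The subgroup and sensitivity paragraph of the same section repeats the primary and key secondary analyses with missing data "considered as nonresponses, by carrying forward the baseline values". Definitions of Analysis Sets confirms it: "an additional analysis set for a sensitivity analysis will be constructed with missing data for study endpoints treated as nonresponses".

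The per-protocol (as-treated) set keeps only adherent completers, so it does not probe the missing-data assumption. No delta-adjusted, tipping-point or reference-based analysis is described. Expected dropout is about 15% overall, with no split by arm.

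**The concern.** Carrying baseline forward is often read as a cautious choice, because someone who leaves is credited with no benefit. That holds for a responder endpoint. For a change score it holds only in some circumstances. The rule removes improvement from whoever is missing, in either arm. If both arms improve and placebo loses more people, it removes more improvement from placebo and makes aspirin look better.

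This is the only analysis in the plan that changes the missing-data assumption for all randomized participants. A positive primary result that also passes it would probably be reported as robust to missing data. That conclusion needs a check whose direction is known, or one that shows how large a departure would overturn the result. Carry-forward provides neither.

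**Working it through.** **Inputs from Section VI.C:** 80 randomized; 15% dropout, leaving 68; difference 3 points; SD of change s = 2.45; two-sided 0.05. **Assumed, because the documents do not give them:** 1:1 allocation (40 per arm), mean change in each arm, dropout in each arm, and dropout unrelated to outcome. Negative change is improvement, and a negative difference (aspirin minus placebo) favours aspirin.

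**1. The plan's own figure.** 80 × 0.85 = 68, or 34 per arm. SE = 2.45 × √(2/34) = 0.594; z = 3/0.594 = 5.05; power = Φ(5.05 − 1.96) = 99.9%. The statement that "the probability is >90% that the study will detect a treatment difference" is met.

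**2. What carry-forward estimates.** With mean change m and missing share p in an arm:
- mean = (1 − p)m
- variance = (1 − p)s² + p(1 − p)m², with s² = 6.0025

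With no drug effect (m the same in both arms), bias = m × (p_placebo − p_aspirin).

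**3. No drug effect, both arms changing by −2 (assumed).**

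*Dropout 5% aspirin, 25% placebo.* Bias = −2 × 0.20 = −0.40. Variances: 5.702 + 0.190 = 5.892 and 4.502 + 0.750 = 5.252. SE = √(11.144/40) = 0.528, so z shifts by −0.76. False positives favouring aspirin = Φ(−1.96 + 0.76) ≈ 11.5%; simulation gives 11.7%.

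*Dropout 10%, 20%.* Bias = −0.20; SE = √(11.204/40) = 0.529; shift −0.38. Favouring aspirin ≈ 5.7%; two-sided ≈ 5.7% + 1.0%, or about 6.6%.

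| Dropout, aspirin / placebo | Bias (points) | One-sided false positives favouring aspirin |
|---|---|---|
| 5% / 25% | −0.40 | about 12% |
| 10% / 20% | −0.20 | about 5.7% |
| equal | 0 | 2.5% |
| 25% / 5% | +0.40 | about 0.3% |

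In ANCOVA simulations of the 5% / 25% case (assumed baseline SD 6; slope of change on baseline 0, −0.2 or −0.3), the one-sided rate was 11.6%, 13.1% and 16.7%. The completers' analysis of the same data stayed at 2.3% to 2.4%. Control-based imputation in this scenario had about zero bias and a rate of about 2%.

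**4. Planned effect, −3 against 0.**
- Equal 15% dropout: estimate −3 × 0.85 = −2.55; SE = √((6.250 + 5.102)/40) = 0.533; z = 4.79, against 5.05 for completers. The effect is diluted and the test is harder to pass.
- 10% / 20%: estimate −2.70; SE 0.525; z = 5.15, against 5.04 for completers. The check looks slightly stronger than the analysis it is meant to challenge.
- Full-data SE for comparison: 2.45 × √(2/40) = 0.548.

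**5. Why it is not a bound.** Relative to missing at random, carry-forward under −3 against 0 adds 3 points to each aspirin dropout and nothing to each placebo dropout. The penalty is set by the arm means and not by a judgement of what is plausible. If only aspirin dropouts are penalized, with 15% missing and the SE held at 0.594, the penalty that removes significance is (3 − 1.96 × 0.594)/0.15 ≈ 12 points. For an assumed observed effect of −1.5 it is (1.5 − 1.164)/0.15 ≈ 2.2 points, more than the 1.5 points that carry-forward would impose with an unchanged placebo arm. A tipping-point table reports these distances; carry-forward does not.

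**The case against.** **The harmful pattern is one direction among several.** The tolerability risks in Sections V.B and VI.A (bleeding, aspirin intolerance, GI upset) lie mainly on aspirin, and placebo is described as well tolerated. If aspirin loses more people while both arms improve, carry-forward works against aspirin. This stands. The documents do not forecast dropout by arm or change on placebo, so neither direction can be presumed. If both arms worsened, greater aspirin dropout would favour aspirin, though an assumed 1-point worsening with 20% against 10% gives only −0.10 points.

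**A reader might infer that the carry-forward SE is too small, since filled-in zeros count as observations.** The working does not support this. In simulation its reported SE (0.531) matched its actual sampling SD (0.533), and with equal dropout type I error was 5%. The SE is correct for the estimator the plan defines. Under −3 against 0 it does fall below the full-data value (0.53 against 0.55), but this is not general. At −4 against −1 it is √((7.142 + 5.230)/40) = 0.556, and in ANCOVA with slope −0.3 it was 0.409 against 0.373.

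**The contrast with control-based imputation can be overdrawn.** Under −3 against 0 both methods estimate about −2.55. The larger Rubin's-rules SE (0.617) exceeds that estimator's own sampling SD (0.541), so much of the gap in z is caution built into Rubin's rules.

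**The role is secondary.** The plan does not call carry-forward a worst case. The Early Termination visit, open to those with at least 11 weeks on drug, repeats the month-6 assessments and may reduce missingness. Both points limit the consequence. Neither supplies a check on missing at random.

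**Conclusion.** The point holds in limited form. For the continuous primary and key secondary endpoints, carry-forward is a single scenario: its direction depends on arm-level dropout and on change shared by both arms, and it shows no limit on departures from missing at random. With no drug effect and an assumed 2-point improvement in both arms, it moves the estimate toward aspirin by 0.20 points at 10% / 20% dropout and 0.40 points at 5% / 25%, and by the same amounts against aspirin when the pattern is reversed. With equal dropout it dilutes the effect and holds type I error.

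A reader might go further and call the analysis invalid, or treat the primary result as compromised. The documents do not support either. Carry-forward can be a harder test than the primary analysis, it is coherent for the binary endpoint of at least 30% relative reduction, and the primary analysis, sample size and power do not depend on it. What is affected is how much a passed sensitivity analysis would entitle the authors to claim. The sizes rest on assumed 1:1 allocation, assumed arm means and dropout splits, and dropout unrelated to outcome.

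**What to change.** In Section VI.C:

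- Keep missing as nonresponse for the binary endpoint.
- For the continuous endpoints, name as the test of missing at random (a) control-based multiple imputation, with missing aspirin values drawn from the placebo distribution, and (b) a delta-shift tipping-point table built on the multiple imputations already planned, showing the shift at which the conclusion changes.
- Report missingness by arm, and state whether Early Termination scans count as month-6 outcomes.
- Keep carry-forward, if at all, as a supplementary scenario, with a note that its direction depends on the dropout pattern.

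The plan allows finalization up to database lock, so this can be pre-specified if lock has not occurred; afterwards it should be labelled post hoc. The cost is SAP wording and a few hours of programming. The downside is somewhat wide, cautious Rubin's-rules intervals for the control-based analysis.
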